9.2.2.3 Exploratory Endpoints

- Presence, frequency, interference, amount and/or severity of select PRO-CTCAEs tabulated at each cycle
- ASK-12 scores at each assessment time point
- PRO compliance rate defined as the proportion of patients who submit the given PRO instrument among those eligible at each time point which excludes those missing by design (due to death or disease progression, early treatment discontinuation)
- PRO completion rate defined as the proportion of patients who complete given PRO instrument based on the instrument's scoring system among those eligible at each time point

9.3 Statistical Analysis Plan

9.3.1 Primary Clinical Analysis

The primary analysis will be on an intention to treat (ITT) basis considering the randomized treatment assignment irrespective of treatment received. OS will be estimated using the Kaplan-Meier (KM) method and compared using a stratified log-rank test. Stratified Cox proportional hazards regression will produce a treatment hazard ratio (HR) estimate (ixazomib-lenalidomide/placebo-lenalidomide). Interim analyses for efficacy will be conducted. The design incorporates a group sequential monitoring plan with 6 interim analyses (IA) and one final analysis for the OS comparison between arms. Based on accrual and failure rate assumptions in the sample size calculation (Section 9.4), interim analyses are expected to occur from 3y to 5.5y after randomization and the final analysis at full information (179 deaths) is expected to occur after 6y of follow-up. Critical values as presented below in Table 1 are based on the Lan-DeMets error spending rate function corresponding to the truncated version of O'Brien-Fleming boundaries to preserve the overall type I error rate. At each interim analysis, the null hypothesis of equal OS on the two arms will be tested against the 1-sided alternative of increased OS on the ixazomib-lenalidomide arm. The p-value from a 1-sided stratified log-rank test will be compared to the level of nominal significance associated with these critical values. If the boundary is crossed at an IA, there is sufficient evidence of efficacy to stop the study in favor of the alternative hypothesis. The DSMC then would consider stopping the study early.

Table 1

Analysis	Study Time (years)	Information Time (%)	Failures under Alternative	Critical Value	Nominal Significance
1	3.0	35%	63	3.2905	0.0005
2	3.5	47%	84	3.1768	0.0007
3	4.0	59%	105	2.7443	0.0030
4	4.5	70%	126	2.4984	0.0062
5	5.0	81%	145	2.3232	0.0101
6	5.5	91%	162	2.1904	0.0142
7	6.0	100%	179	2.0858	0.0185

Coupled with the interim analysis for early stopping for superiority of ixazomib-lenalidomide (Arm A), the study will be monitored for harm and inefficacy. At 35% information, the DSMC may consider stopping the study early for harm if the lower bound of a 95% confidence interval for the HR is above 1.0. Interim inefficacy monitoring is planned to start after approximately 47% of full information becomes available with repeated analysis at each semi-annual DSMC meeting. The Linear 20% Inefficacy Boundary (LIB20), an approach described by Freidlin et al, will be used.⁷¹ The study may be stopped if there is

not at least a small trend in favor of the alternative hypothesis starting at this time. Specifically, at each interim analysis, if the estimated HR is larger than the cutoff value given in the LIB20 boundary (Table 2), the DSMC then would consider stopping the study early for lack of efficacy.

Table 2

Information Proportion	Cutoff Hazard Ratio
47%	1.004
59%	0.984
70%	0.965
81%	0.947
91%	0.931
100%	0.917

9.3.2 Secondary Clinical Analyses

Progression-Free Survival (PFS)

An important secondary aim is to evaluate whether a response-adapted strategy translates into superior progression-free survival for patients switching to more-intensive treatment. PFS will be estimated using the KM method and compared using the stratified log-rank test. Median PFS on the control arm is assumed to be 18 months based on results from recent clinical trials. Assuming exponential distribution of failures, this study is design to detect a 44% increase in median PFS to 26 months on the experimental arm. This corresponds to a treatment HR approximating 0.70 [monthly hazard rate 0.0385 versus 0.0267]. At 1-sided 2.5% type I error, there is approximately 90% power using a log-rank test to detect this HR given 510 patients uniformly accrued over 3.5y with full information of 319 PFS events at 4.5y (accrual end plus one year). The actual timing of this PFS analysis will depend on accrual. The analysis will not be done before one year after the last patient is randomized. No interim analyses for the PFS comparison will be conducted. The study team will also not consider or declare the experimental arm to be a success based on the PFS endpoint alone.

Response

Response will be tabulated by category. Response rates (sCR, CR, VGPR) will be compared using the chi-squared test for proportions. It is hypothesized that the ixazomib-lenalidomide arm will have higher response rates. Ineligible patients are excluded from the analysis and unevaluable patients are counted in the denominator. Sensitivity analyses will exclude unevaluable patients from the rate calculations. Given 255 patients per arm, there is over 90% to detect a difference of 15% in VGPR rates at 1-sided 2.5% significance assuming a 52.5% overall VGPR rate.

Toxicity

We will monitor the toxicities experienced by all treated patients. Interim analyses of toxicity are performed twice yearly for all ECOG-ACRIN studies. Expedited reporting of certain adverse events is required, as described in Section [5.3](#). We are specifically interested in comparing the rates of worst grade 3 or higher non-hematologic treatment-related events using the chi-squared test for proportions. It is likely that the ixazomib-lenalidomide arm will have moderately higher toxicity rates than the placebo-lenalidomide arm. The grade 3 or higher treatment-related non-hematologic rate on the placebo-lenalidomide arm is estimated to be around 36% based on reported toxicity rates on the lenalidomide arm of the CALGB maintenance trial. Assuming 1-sided 2.5% significance, there is 84% power to detect a difference in grade 3 or higher treatment-related non-hematologic rates of 13% (ixazomib-lenalidomide arm 49% rate) with all enrolled patients treated. The maximum width of a 95% CI for a rate of a given toxicity on either treatment arm is 13%. As exploratory, global grade 3 or higher treatment-related non-hematologic rates will be evaluated within age subgroups dichotomized at 65 years. We also plan to examine comprehensively adverse events experienced by study participants using the Tox-T method which has been validated as a tool to assess adverse events in other NCTN trials.⁴⁶

9.3.3

Exploratory Clinical Endpoints

Time to Progression and Duration of Response

TTP and DOR in each arm will be estimated using the Kaplan-Meier method.

Treatment Exposure

Treatment exposure to the oral medications lenalidomide and ixazomib will be quantified using patient medication calendars. Cumulative dose, dose intensity, and relative dose intensity will be calculated overall and by cycle. Data will be summarized by treatment arm with descriptive statistics and graphically over time. Treatment duration in each arm will be estimated using the Kaplan-Meier method. Patients will be classified into dichotomous groups based on a 75% relative dose intensity cutoff (< 75% vs \geq 75% represents poor vs good treatment adherence). The proportion of patients with poor lenalidomide treatment adherence will be compared between arms using the chi-squared test for proportions. In addition, multivariable logistic regression analysis will be conducted to identify the baseline factors associated with calculated good treatment adherence. We will conduct one interim analysis to monitor treatment adherence to ixazomib. Specifically, the treatment adherence rate at 18 months will be measured by ixazomib relative dose intensity at or exceeding 75% ("good" treatment adherence). This analysis is expected to occur at 2.5 years from randomization when 72 patients (29% of target accrual) have reached potentially 18 months of assigned ixazomib therapy. If the treatment adherence rate is at least 80% we would consider this acceptable while a treatment adherence rate of 65% is considered evidence that adherence to ixazomib is unacceptable. If

54 or more patients achieve target treatment adherence exceeding 75% over 18 months, then the study will continue. If the true treatment adherence rate is 65%, the probability of concluding treatment adherence is acceptable is 0.05 (type I error). If the true treatment adherence rate is 80%, the probability of concluding treatment adherence is acceptable is 0.88 (power).

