5.1 Administration Schedule

NOTE: All patients should be on at least 81 mg acetylsalicylic acid (ASA) daily while receiving lenalidomide. Please see Section [5.6.16](#) for additional information regarding thromboprophylaxis.

5.1.1 **Arm X (Arms A and B)**

NOTE: Patients are randomized to Arm A (lenalidomide and ixazomib) or Arm B (lenalidomide and placebo) but will be identified as on Arm X as this is a blinded trial.

Lenalidomide: 10 mg PO daily days 1-28

NOTES: For patients with creatinine clearance 30-60 mL/min lenalidomide dose will be reduced to 5 mg PO daily.

Lenalidomide may be taken with or without food. Capsules must not be crushed, chewed, or opened.

Please refer to Section [8.2](#) for additional Lenalidomide administration details.

Ixazomib/Placebo: 4 mg PO days 1, 8, and 15

Repeat cycle every 28 days until disease progression or unacceptable toxicity.

NOTES: Ixazomib/Placebo capsule(s) must be taken on an empty stomach, 1 hour before or 2 hours after food. Capsule(s) must be swallowed whole with water. Do not open or break capsules.

Missed or delayed doses can be taken only if the next scheduled dose is \geq 72 hours away. A missed dose should not be taken within 72 hours of the next scheduled dose. If vomiting occurs after taking a dose, the patient should not repeat the dose. Resume dosing at the time of the next scheduled dose.

Please refer to Section [8.1](#) for additional Ixazomib/Placebo administration details.

Rev. Add3

Rev. Add3

Rev. Add3

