9.2.1.2 Secondary Endpoints

- Progression-free survival defined as the time from randomization until the earlier of progression or death due to any cause, or censored at date of last disease evaluation (Note: Only deaths that occur within 3 months of the last disease evaluation are considered events.)
- Best response on treatment for eligible patients based on standard IMWG criteria as described in Section 6; Response rates for eligible patients including very good partial response (VGPR), complete response (CR) and stringent CR (sCR) at 12-, 24-, 36- and 60-cycles post-randomization
- Incidence of adverse events by worst grade and type for treated patients determined using CTCAE; Rates of worst grade 3 or higher non-hematologic toxicity and overall worst grade 3 or higher toxicity on treatment

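### The grade 3+ toxicity test measures total on-treatment burden and cannot separate a higher toxicity rate from a difference in time on treatment

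*Combined protocol and SAP*

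**What the plan says.** The formal comparison is in Section 9.3.2 (Toxicity): "We are specifically interested in comparing the rates of worst grade 3 or higher non-hematologic treatment-related events using the chi-squared test for proportions". The endpoint in Section 9.2.1.2 is: "Rates of worst grade 3 or higher non-hematologic toxicity and overall worst grade 3 or higher toxicity on treatment". It sets no time window. (It also lacks the treatment-related qualifier; I follow Section 9.3.2, where the test is described.) Section 5.1 sets the length of treatment: "Repeat cycle every 28 days until disease progression or unacceptable toxicity".

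The design does not expect equal time to progression. In Section 9.3.2 (PFS): "Median PFS on the control arm is assumed to be 18 months based on results from recent clinical trials", with a target of 26 months on the experimental arm and exponential failure times.

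On power: "Assuming 1-sided 2.5% significance, there is 84% power to detect a difference in grade 3 or higher treatment-related non-hematologic rates of 13" percentage points.

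Two other parts of the plan bear on exposure. Section 9.3.2 adds a Tox-T analysis, which the title of its cited source describes as longitudinal. Section 9.3.3 plans Kaplan-Meier estimates of treatment duration and dose-intensity summaries by arm, under exploratory endpoints. Neither is specified as an exposure-adjusted contrast of grade 3+ events between arms.

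**The concern.** A patient who stays on treatment longer has more time in which to have a first grade 3+ event. When treatment runs to progression and one arm is expected to progress later, the on-treatment proportion can rise in that arm even if its toxicity rate per month is no higher. If that arm stops earlier for other reasons, the proportion can fall and mask a higher monthly rate.

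The safety objective (Section 2.2.3) concerns the safety profile of ixazomib added to lenalidomide. Readers will want to know both how much toxicity patients accumulate under each strategy and whether adding ixazomib raises the rate while on treatment. The planned test answers the first question. Nothing pre-specified answers the second.

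**Working it through.** **Inputs from the plan.** Control rate: "rate on the placebo-lenalidomide arm is estimated to be around 36" per cent. Experimental rate and population: "ixazomib-lenalidomide arm 49% rate) with all enrolled patients treated". Arm size, from the response paragraph of Section 9.3.2: "Given 255 patients per arm". One-sided 2.5% test. Median PFS 18 and 26 months, exponential. Uniform accrual over 3.5 years, PFS analysis at 4.5 years (Section 9.3.2), final OS analysis at 6 years (Section 9.4).

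**Assumptions not in the plan.** The toxicity hazard h is constant and equal in both arms, exposure ends at progression, and h is set to give 36% in the control arm.

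**1. The plan's power figure.** The pooled proportion is 0.425. The null SE is √(2 × 0.425 × 0.575 / 255) = 0.0438. The alternative SE is √((0.36 × 0.64 + 0.49 × 0.51) / 255) = 0.0434. Power = Φ[(0.13 − 1.96 × 0.0438) / 0.0434] = 0.846. The stated 84% reproduces.

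**2. Expected time to progression.** λ = ln 2 / median = 0.0385 (Arm B) and 0.0267 (Arm A) per month. Means are 1/λ = 26.0 and 37.5 months, ratio 1.44.

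**3. Crude proportion under equal monthly hazards.** With follow-up t, P = h/(h + λ) × [1 − exp(−(h + λ)t)]. Followed to progression, h = 0.0385 × 0.36/0.64 = 0.0217, and Arm A is 0.0217/(0.0217 + 0.0267) = 44.8%. For a data cut at T months, P is averaged over t from T − 42 to T and h is recalibrated to 36%. For early toxicity, t is the length of the period in which events can occur.

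| Situation | Arm B | Arm A | Gap (points) | Chance that the test rejects |
|---|---|---|---|---|
| Followed to progression | 36% | 44.8% | 8.8 | 0.53 |
| 6-year cut | 36% | 42.7% | 6.7 | 0.34 |
| 4.5-year cut | 36% | 41.1% | 5.1 | 0.22 |
| Hazard in first 24 months only | 36% | 40.1% | 4.1 | 0.16 |
| First 12 months only | 36% | 38.2% | 2.2 | 0.075 |
| First 6 months only | 36% | 37.1% | 1.1 | 0.045 |

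**4. Other reasons for stopping (assumed rates).** Adding 1% to 3% per month in both arms gives Arm A 42.7% to 40.5% if followed to progression, and 40.5% to 39.6% at the 4.5-year cut. If only Arm A has the extra stopping, about 1.2% per month (0.0385 − 0.0267) removes the gap. At 2% per month Arm A falls to 31.7%, a gap of −4.3 points.

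**5. What an observed 36% versus 49% could mean.** With equal exposure, the hazard ratio is (0.49/0.51)/(0.36/0.64) = 1.71. With 18 versus 26 months it is 0.0256/0.0217 = 1.18 if followed to progression, 1.25 at 6 years and 1.32 at 4.5 years. The planned test does not distinguish these.

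**6. Fixed windows.** Twelve 28-day cycles are 11.0 months and 24 are 22.1 months. With h = 0.0217 and treatment end as a competing event:

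| Window | Arm B | Arm A, equal hazard | Chance of rejection | Power if 36/49% arises with 18/26 months | Power if it arises with equal exposure |
|---|---|---|---|---|---|
| Cycle 12 | 17.5% | 18.5% | 0.05 | 21% | 79% |
| Cycle 24 | 26.5% | 29.4% | 0.11 | 41% | 89% |

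**The case against.** The strongest reply is that the comparison is randomized and double-blind, so a difference in on-treatment proportions is an effect of assignment, including any part that comes through longer treatment. Section 2.2.3 asks for toxicity rates to be compared between arms, and for treatment given to progression the cumulative burden per patient is a legitimate answer. This stands. A reader might infer that the trial cannot attribute a difference to ixazomib, or that 0.53 is a false-positive rate. The documents support neither reading: if the true proportions are 36% and 44.8%, the null hypothesis of the chi-squared test is false, and rejecting it is correct for the quantity it tests.

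The 8.8-point figure is also an upper case. It needs follow-up of every patient to progression, no other reason for stopping, and a hazard that persists for years. Section 5.7 lists other reasons. In the phase II study of this combination described in Section 1.3, 14 of the 30 patients off study left through consent withdrawal (11) or investigator discretion (3). Section 5.6.9 says that rash, when it occurs, tends to appear in the first three cycles. These points justify a range and leave the direction of the gap uncertain. They do not show that exposure will be balanced.

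Finally, Tox-T, the treatment-duration summaries and the cycle-12 neurotoxicity score comparison (Section 9.3.4) all help interpretation. The first two lack a defined between-arm contrast for grade 3+ events, and the third is a patient-reported score covering one domain. The test is secondary, and no stopping or success rule depends on it, which limits the consequence.

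**Conclusion.** The point holds as one of interpretation and incomplete specification; the power arithmetic is correct. The only formal grade 3+ comparison is a crude proportion over a period that ends at progression. It measures burden and does not isolate the toxicity rate per unit of exposure.

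Under the plan's PFS target and the assumptions listed under the working, exposure alone could supply 5 to 9 of the planned 13 points, or 1 to 4 if toxicity is confined to the first 6 to 24 months. Higher discontinuation in Arm A could cancel or reverse this. The documents do not settle which case applies, so neither the direction nor the size of the exposure effect can be fixed in advance.

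A reader might go further and conclude that the chi-squared test is invalid or must be demoted. The documents do not support that: it answers the burden question, and its stated power is right for that question.

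**What to change.** Keep the chi-squared test and its 84% power in Section 9.3.2, and label it as total on-treatment burden. Before unblinding, pre-specify beside it:

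- the cause-specific hazard ratio for first grade 3+ treatment-related non-hematologic event while on treatment (or the exposure-adjusted rate ratio), with 95% CI;
- cumulative incidence of that event by arm at the end of cycles 12 and 24, with end of treatment without an event as a competing event, and the difference with 95% CI.

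The hazard or rate ratio is needed as well as the windows, because the cycle-24 window still leaves a 2.9-point gap under equal hazards (26.5% versus 29.4%). Do not attach 84% to the fixed-window proportions. In the working, power for them runs from 21% to 89% depending on the window and on how the 36% and 49% arise, so any figure quoted must be recalculated.

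Cost: SAP wording and one additional standard analysis. Section 5.3.5 already collects adverse events by treatment course, so no new data or patients are needed. Downsides: the windows contain fewer events and leave out late toxicity, and the rate ratio assumes a roughly constant hazard.

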9.3.4 Patient-Reported Outcomes (PRO) Endpoints

PRO compliance and completion rates will be tabulated at each collection time point and overall separately for the FACT-G (FWB and PWB subscales), FACT-Ntx, FACT-MM, ASK-12 and PRO-CTCAE instruments.

Health-Related Quality of Life (QOL)

To assess the impact of treatment and disease on health-related QOL, there are two co-primary endpoints: change in FACT/GOG-Ntx TOI from baseline to end of cycle 12 post-randomization (beginning of cycle 13 assessment) and change in FACT-MM TOI from baseline to end of cycle 24 (beginning of cycle 25 assessment) post randomization. The FACT-G (FWB and PWB subscales), Ntx and MM will be administered at the beginning (day 1) of every 3 cycles for the first 24 cycles (beginning of cycles 4, 7, 10, 13, 16, 19, 22 and 25) and every 6 cycles thereafter (up to completion of 48 cycles of therapy (beginning of cycles 31, 37, 43, and 49), or at treatment discontinuation prior to completion of 48 cycles of therapy. During long-term follow-up/post-treatment end, there will be four quarterly assessments for 1 year. We hypothesize that treatment with ixazomib will not result in a significant difference in the FACT/GOG-Ntx TOI over the first 12 cycles and that improved PFS will result in higher FACT-MM TOI scores by end of 24 cycles. All patients who receive at least one dose of study drug and complete the QOL assessment at both time points are eligible. Power calculations are based on t-tests comparing the two treatment arms for the change in score with a 2-sided 0.05 alpha split between these comparisons. In an unselected group of MM patients being treated with oral therapy (n=118), the FACT-MM TOI had a standard deviation (SD) of approximately 21 points. The FACT-Ntx TOI has a reported SD of 14-16.⁷⁰ We propose using a general effect size measure of half standard deviation to establish the minimally important difference (MID).^{47,69} We therefore will establish a MID of 10 for the FACT-MM TOI and 8 for the FACT-Ntx TOI. We assume 90% and 81% of patients are alive by year 1 and 2, respectively, as well as a 10% drop-out rate resulting in potential patients of n=414 and n=373 for each analysis. Sensitivity for the proportion assumed to submit the questionnaire at both time points (compliance rates of 60% and 80%), allowing for a range of instrument variability and assuming different correlation (0.6, 0.4) between repeated measures was performed (Table 3). The difference in the FACT-Ntx TOI mean change score over 12 cycles of treatment between the ixazomib-lenalidomide arm and the placebo-lenalidomide arm that can be detected with 80% power at 2-sided 0.025 significance level ranges from 3.7-6.9 points as shown below. The difference in the FACT-MM TOI mean change score over 24 cycles of

treatment between the ix-a lenalidomide arm and the placebo-lenalidomide arm that can be detected with 80% power at 2-sided 0.025 significance level ranges from 5.8-10.0 points. All of the scenarios show the target MID for each comparison or smaller can be detected with satisfactory power and thus we will be able to show a significant difference in QOL if it occurs.

Table 3

			Differences in FACT-Ntx TOI Subscale Mean Change Score (power=80%, 2-sided alpha=0.025)	
Standard Deviation (SD)	Correlation	SD of change	60% compliance (n=124/arm)	80% compliance (n=164/arm)
From Baseline to 12 Cycles Post Randomization				
12.0	0.6	10.7	4.2	3.7
	0.4	13.1	5.2	4.5
14.0	0.6	12.5	4.9	4.3
	0.4	15.3	6.0	5.3
16.0	0.6	14.3	5.6	4.9
	0.4	17.5	6.9	6.0
Differences in FACT-MM TOI Mean Change Score (power=80%, 2-sided alpha=0.025)				
Standard Deviation (SD)	Correlation	SD of change	60% compliance (n=112/arm)	80% compliance (n=148/arm)
From Baseline to 24 Cycles Post Randomization				
18.0	0.6	16.1	6.7	5.8
	0.4	19.7	8.2	7.1
20.0	0.6	17.9	7.4	6.4
	0.4	21.9	9.1	7.9
22.0	0.6	19.7	8.2	7.1
	0.4	24.1	10.0	8.7

Sensitivity analysis will be conducted to retain patients who discontinued treatment early and missing their FACT-Ntx TOI score after 12 cycles of treatment (beginning of cycle 13 assessment) using their QOL score at early treatment discontinuation for the analysis. For the FACT-MM TOI analysis after 24 cycles of treatment (beginning of cycle 25 assessment) the long-term follow-up assessment closest to 2 years from randomization will be used if patients are not on treatment. Descriptive statistics (mean, SD, median, range) will be used to evaluate the distribution of levels and

changes for the set of health-related QOL evaluations including the FACT/GOG-Ntx TOI, FACT-MM TOI and FACT-G (FWB and PWB subscales). Levels and changes will also be assessed graphically. Linear mixed effects models will be used to perform repeated measured regression analysis with the assumed covariance matrix maximizing Akaike information criteria. Models with treatment, assessment time, and treatment by assessment time interaction with and without other predictors will be fit. If there is substantial missingness, we will analyze the data according to the methods described in Schluchter and Schluchter, Greene and Beck. These methods consider missingness informative by jointly modeling longitudinal QOL score and survival time to dropout.

There are two key secondary health-related QOL analysis comparing treatment arms: Time to worsening of the FACT/GOG-Ntx TOI and time to improvement of the FACT-MM TOI. Time to worsening of the FACT/GOG-Ntx TOI and time to improvement of the FACT-MM TOI will be analyzed with the KM method and compared using the log-rank test. We will establish significance as alpha=1.67% based on Bonferroni adjustment (5% divided over 3 comparisons). We will provide rates on each arm including exact binomial 95% confidence intervals for the FACT/GOG-Ntx TOI recovery rate and FACT-MM TOI response rate.

As exploratory, correlation between time to worsening of symptoms with PFS and OS will be assessed with Kendall's Tau adjusted for censored observations.

Finally, we will evaluate whether patients with poor treatment adherence based on medication calendars and lower likelihood of medication adherence based on ASK-12 scores have lower QOL scores [the FACT/GOG-Ntx TOI, FACT-MM TOI and FACT-G (FWB and PWB subscales)] after 12- and 24-cycles of treatment. Linear regression analysis at these 2 time points separately will be conducted with QOL score as outcome and treatment adherence group as the main effect adjusting for baseline QOL score along with other disease and demographic characteristics.

PRO-CTCAE

Analyses related to the PRO-CTCAE are exploratory. Descriptive statistics will be used to summarize selected PRO-CTCAEs tabulated at each cycle overall and by arm. We will map PRO-CTCAEs with provider reported AEs and evaluate differences in incidence and worst severity. PRO-CTCAE ratings will further be evaluated in relation to patient bother by treatment side effects (FACT-GP5 item, "I am bothered by treatment side effects") to identify the toxicities that are most highly associated with treatment tolerability issues.

Medication Adherence Scale

Analyses related to the ASK-12 are exploratory. Descriptive statistics will be used to summarize ASK-12 scores tabulated every 6 cycles on study therapy. The ASK-12 is reported to have a mean (standard deviation) of 27.5 (7.2). Differences between arms will be evaluated

based on the t-test (or Wilcoxon rank sum test). Patients will also be classified into high versus low likelihood of medication adherence groups according to tertile distributions (lowest tertile vs second and top). The relationship between likelihood of medication adherence and calculated treatment adherence dichotomous groups will be evaluated in 2x2 tables. In addition, multivariable logistic regression analysis will be conducted to identify the baseline factors associated with low likelihood of medication adherence over 12- and 24-cycles of treatment.

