2.4 Patient-Reported Outcomes (PRO) Objectives

2.4.1 Primary PRO Objectives

2.4.1.1 To quantify the extent to which the addition of ixazomib to lenalidomide maintenance contributes to neuropathy and associated physical and functional impairments.

2.4.1.2 To assess the impact of the addition of ixazomib to lenalidomide maintenance on disease control and associated physical and functional well-being.

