9.2.2.2 Secondary Endpoints

- Levels and changes from baseline of all instruments
- Time to worsening of FACT/GOG-Ntx TOI defined as the time from baseline to a decrease of 8 points (MID), respectively, or censored at the date of last assessment
- FACT/GOG-Ntx TOI recovery rate in the patients experiencing a MID decrease, the proportion of patients with the FACT/GOG-Ntx TOI score returning to baseline level
- Time to improvement of the FACT-MM TOI defined as the time from baseline to an increase of 10 points (MID), respectively, or censored at the date of last assessment
- FACT-MM TOI response rate defined as the proportion of patients experiencing a MID improvement since baseline at each assessment time point

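### Key secondary PRO tests: alpha is 5% over three comparisons but only two are named; and the neurotoxicity co-primary, hypothesised as no significant difference, has no planned between-arm interval

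*Combined protocol and SAP*

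**What the plan says.** **Key secondary PRO tests (9.3.4).** The section announces two key secondary quality-of-life analyses comparing the arms, time to worsening of the Ntx TOI and time to improvement of the MM TOI. Each uses Kaplan-Meier estimates and a log-rank test. The next sentence sets alpha at 1.67% by Bonferroni, with 5% shared by three comparisons. The Ntx recovery rate and the MM response rate follow, as per-arm rates with exact binomial 95% intervals.

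**Ntx co-primary (9.3.4).** The hypothesis is "We hypothesize that treatment with ixazomib will not result in a significant difference in the FACT/GOG-Ntx TOI over the first 12 cycles". The test appears in the power text: t-tests on change scores, with a two-sided 0.05 split over the two co-primary endpoints, so 0.025 each. The analysis set is "All patients who receive at least one dose of study drug and complete the QOL assessment at both time points are eligible". The MID is 8 points for the Ntx TOI. After giving the detectable differences, the plan concludes "thus we will be able to show a significant difference in QOL if it occurs".

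Supporting analyses are also planned: "Sensitivity analysis will be conducted to retain patients who discontinued treatment early and missing their FACT-Ntx TOI score after 12 cycles of treatment", using the score at discontinuation; "Linear mixed effects models will be used to perform repeated measured regression analysis"; and joint models if missingness is substantial. Objective 2.4.1.1 is worded as estimation: "To quantify the extent to which the addition of ixazomib to lenalidomide maintenance contributes to neuropathy".

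**The concern.** **Alpha count.** A stated decision threshold disagrees with the list of tests it governs. Either a comparison is missing from the text or the divisor is wrong. Until that is settled, a p-value between 1.67% and 2.5% on either key secondary test cannot be classified.

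**Ntx co-primary.** When the hypothesis is that no significant difference will appear, a non-significant p-value fulfils it as worded. Non-significance does not show how large a deficit the data still allow. 9.3.4 plans no between-arm confidence interval for the difference in mean change, and an interval is what would show it. Section 9.3.2 expects more toxicity on the ixazomib arm ("It is likely that the ixazomib-lenalidomide arm will have moderately higher toxicity rates than the placebo-lenalidomide arm"). That sentence concerns clinician-graded toxicity rates rather than mean Ntx TOI, but it makes the size of any deficit a question readers will ask.

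**Working it through.** **1. Alpha for the key secondary tests**

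- Plan's figure: 0.05/3 = 0.01667, which reproduces 1.67%.
- Tests named: two. Alpha spent: 2 × 0.01667 = 3.33% of the 5%. With two tests, Bonferroni gives 0.05/2 = 2.5% each.
- Power lost: take a test with 80% power at two-sided 1.67%. Its standardised effect is z(0.99167) + z(0.80) = 2.394 + 0.842 = 3.236. At two-sided 2.5% the critical value is z(0.9875) = 2.241, so power is Φ(3.236 − 2.241) = Φ(0.994) = 84%. The plan does not state sidedness here. If one-sided, the result is Φ(2.128 + 0.842 − 1.960) = 84% as well. The 80% starting point is an assumption, because the plan gives no power for these tests.
- Candidates for a third comparison: the recovery and response rates are the other analyses beside these two, but 9.3.4 describes them per arm and states no between-arm test. The documents do not identify a third test.

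**2. Ntx co-primary**

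Inputs from 9.3.4 and Table 3: SD 12, 14 or 16; correlation r of 0.6 or 0.4; n of 124 or 164 per arm; two-sided alpha 0.025; power 80%; MID 8. Formulas, using the normal approximation:

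- SE = SD × √(2(1 − r)) × √(2/n)
- Detectable difference = SE × (2.2414 + 0.8416)
- Chance of non-significance at a true deficit d = Φ(2.2414 − d/SE) − Φ(−2.2414 − d/SE)
- Largest deficit inside the 97.5% interval when the result is just non-significant = 2 × 2.2414 × SE

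Example (SD 16, r 0.4, n 124): SE = 16 × √1.2 × √(2/124) = 2.226. Detectable difference = 2.226 × 3.083 = 6.86. Miss rate at 8 = Φ(2.2414 − 3.594) = 8.8%. Largest deficit = 2 × 2.2414 × 2.226 = 9.98.

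| SD | r | n/arm | SE | Detectable: computed / Table 3 | Non-significant if true deficit is 8 | Largest deficit in interval |
|---|---|---|---|---|---|---|
| 12 | 0.6 | 124 | 1.363 | 4.20 / 4.2 | <0.1% | 6.11 |
| 12 | 0.6 | 164 | 1.185 | 3.65 / 3.7 | <0.1% | 5.31 |
| 12 | 0.4 | 124 | 1.669 | 5.15 / 5.2 | 0.5% | 7.48 |
| 12 | 0.4 | 164 | 1.452 | 4.48 / 4.5 | <0.1% | 6.51 |
| 14 | 0.6 | 124 | 1.590 | 4.90 / 4.9 | 0.3% | 7.13 |
| 14 | 0.6 | 164 | 1.383 | 4.26 / 4.3 | <0.1% | 6.20 |
| 14 | 0.4 | 124 | 1.948 | 6.00 / 6.0 | 3.1% | **8.73** |
| 14 | 0.4 | 164 | 1.694 | 5.22 / 5.3 | 0.7% | 7.59 |
| 16 | 0.6 | 124 | 1.817 | 5.60 / 5.6 | 1.5% | **8.15** |
| 16 | 0.6 | 164 | 1.580 | 4.87 / 4.9 | 0.2% | 7.08 |
| 16 | 0.4 | 124 | 2.226 | 6.86 / 6.9 | 8.8% | **9.98** |
| 16 | 0.4 | 164 | 1.936 | 5.97 / 6.0 | 2.9% | **8.68** |

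Table 3 reproduces to within 0.1 point in every Ntx cell. With t critical values, the worst miss rate at 8 points is 9.1%, and the four bold entries run from 8.20 to 10.04. In the other eight cells, any non-significant result excludes an 8-point deficit.

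**The case against.** The case against the alpha point is only that it is harmless in direction. That is correct: a reader might infer a type I error problem from the mismatch, but dividing by three for two tests is stricter than needed. The count still contradicts itself.

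The case against the Ntx point is stronger, and much of it stands.

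- A reader might infer that the plan will report p > 0.025 as proof of no impairment. It nowhere says so. The hypothesis can be read as an expectation, the conclusion drawn from Table 3 is about showing a difference if one exists, and objective 2.4.1.1 asks for an estimate.
- A reader might infer that the co-primary is underpowered. At the plan's own MID it is not. Non-significance is much more likely at a true 4-point deficit (13% to 67% across the cells), but nothing in the documents calls 4 points important.
- The four cells that leave 8 points open are mostly the pessimistic ones: three use SD 16 and three use 60% compliance. Even there, the result must fall near the threshold. At a true 4-point deficit, the chance of a non-significant result whose interval still contains an 8-point deficit is 34%, 15%, 14% and 3% in those cells, and zero in the other eight.
- The t-test does not stand alone. Mixed models, the discontinuation-score analysis, joint models and the time-to-worsening test all bear on neurotoxicity, and a mixed model would yield an interval as routine output.

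What remains is that none of these analyses comes with a statement of how the hypothesis will be judged. The reported SD is 14 to 16, and all four open cells lie among the eight cells that use those values.

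**Conclusion.** The alpha point holds on the text alone. Two tests share 5% divided by three, so 1.67 percentage points of the 5% go unspent, at a cost of about 4 points of power for a test that would otherwise have 80%. The documents do not show whether the divisor or the list of tests is wrong.

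The Ntx point holds in a limited form. It is a gap in how the result is to be read, not in power at the MID. Non-significance alone would not support a statement of no impairment, because in 4 of 12 planned scenarios it can coexist with a deficit of the full MID or more. This rests on Table 3's SDs, correlations and sample sizes, and on taking the 0.025 t-test in the power text as the intended co-primary test, since no separate sentence names it as the analysis.

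A reader might also infer that a non-inferiority design is needed. The documents do not call for one. The 8-point MID is a generic half-SD that 9.2.2.2 applies as a within-patient worsening threshold; it is not presented as a between-arm margin.

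Both parts concern PRO endpoints only, and the overall survival conclusion does not depend on them. Severity is minor.

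**What to change.** 1. **Key secondary tests, 9.3.4.** If there are two comparisons, set alpha at 2.5% each. If a third is intended, name it and keep 1.67%. State the sidedness at the same time.
2. **Ntx co-primary, 9.3.4.** State that the conclusion will rest on the between-arm difference in mean change (ixazomib minus placebo) with its 97.5% confidence interval, reported both in the set with scores at both time points and in the planned discontinuation-score sensitivity analysis. Add that p > 0.025 alone will not be taken as support for no impairment.

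The cost is a few sentences, best settled before the PRO results are known. No new data, patients or analyses beyond those planned are needed, and no non-inferiority margin is required.
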